Subjects will enter the study clinic for check-in procedures the day before study drug administration of the first period (Day -1). Mepolizumab will be administered subcutaneously (SC) and reslizumab will be administered intravenously; placebo will be administered either subcutaneously or intravenously (4 subjects each). On Day 1, subjects will receive their assigned treatment according to the randomization schedule.

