5.1.3 Risk/Benefit

Subjects will be informed that participation in a human PK-PD study like the present one cannot be of benefit to healthy volunteers. Nevertheless, the information from the physical examination, vital sign measurements, and ECG results may be shared with the subject's personal physician if this is the subject's choice. Subjects will be informed that it is also their choice to inform their personal physician that they are participating in this research study.

Subjects will be informed that their contribution to the study is of major importance to agencies like the U.S. FDA for helping this agency better evaluate biomarkers. However, since this is a study involving healthy volunteers, subjects will be informed that they have the alternative not to participate.

Subjects will be informed that they may be exposed to risks associated with the pharmacological properties of the investigational product and the study procedures. The following summary of potential AEs for the study drugs will be provided to and discussed with the subjects:

1. Mepolizumab (1)

- Hypersensitivity Reactions: Angioedema, bronchospasm, hypotension, urticaria, and rash have occurred in some subjects receiving mepolizumab. Although the majority of these reactions occurred within hours of drug administration, some instances can have a delayed onset over days.
- Opportunistic Infections: In previous controlled clinical trials, two serious adverse reactions of herpes zoster occurred in subjects receiving mepolizumab.
- Adverse Reactions: The most common adverse reactions include headache, injection site reaction, back pain, and fatigue (incidence $\geq 5\%$).

2. Reslizumab (2)

- Hypersensitivity Reaction: Anaphylaxis occurred with reslizumab infusion in 0.3% of subjects in placebo-controlled trials, although only after the second dose.

- **Malignancy:** In previous placebo-controlled clinical trials, 0.6% subjects receiving 3 mg/kg reslizumab had one or more malignant neoplasm reported. The observed malignancies were diverse and were found in different types of tissue.
- **Adverse Reactions:** The most common adverse reaction is oropharyngeal pain (incidence $\geq 2\%$).

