5.8.1 Treatments Administered

On Day 1, subjects will receive 1 of the following 9 treatments according to the randomization schedule:

- Treatment Group A: Mepolizumab 3 mg, SC
- Treatment Group B: Mepolizumab 6 mg, SC
- Treatment Group C: Mepolizumab 12 mg, SC
- Treatment Group D: Mepolizumab 24 mg, SC
- Treatment Group E: Reslizumab 0.1 mg/kg, IV
- Treatment Group F: Reslizumab 0.2 mg/kg, IV

- Treatment Group G: Reslizumab 0.4 mg/kg, IV
- Treatment Group H: Reslizumab 0.8 mg/kg, IV
- Treatment Group I: Placebo, (4 subjects receive SC and 4 subjects receive IV)

Study drugs will be administered by a clinical research nurse on the study clinic floor at the subject's bedside. The pharmacist and investigator will be available if needed during study drug administration.

Note: Reslizumab must be given as an intravenous infusion only. Do not administer as an intravenous push or bolus.

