5.9. Statistical Methods

5.9.1 Sample Size

Up to 86 healthy subjects will be enrolled (including 14 potential replacement subjects). Subjects will be randomized to one of 9 different active treatment arms (i.e. 8 per treatment arm) and 8 will be randomized to placebo. This sample size was determined empirically based on general sample size requirements for estimating values and variability of PD and PK/PD characteristics that can be used to inform the study design and sample size of future biosimilarity studies.

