5.9.8 Safety Analyses

5.9.8.1 Adverse Events

All AEs will be coded using the latest version of the Medical Dictionary for Regulatory Activities. The incidence of TEAEs, organized by system organ class and frequency, will be summarized by seriousness, severity, relationship to treatment, and by treatment at onset of the TEAE. A detailed listing of serious AEs and TEAEs leading to withdrawal will also be provided.

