7.7. Safety Analyses

7.7.1 Adverse Events

All AEs will be coded using the latest version of the Medical Dictionary for Regulatory Activities (MedDRA). The incidence of TEAEs, organized by system organ class and frequency, will be summarized by seriousness, severity, relationship to treatment, and by treatment at onset of the TEAE. A detailed listing of serious AEs and TEAEs leading to withdrawal will also be provided.

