Attachment B. Randomization Schedule

Subjects will enter the study clinic for check-in procedures the day before study drug administration of the first period (Day -1). Mepolizumab will be administered subcutaneously and reslizumab will be administered intravenously. Placebo will be administered subcutaneously or intravenously to match study drug. On Day 1, subjects will receive their assigned treatment according to the randomization schedule generated by the randomization biostatistician (unblinded and unaffiliated with study data analysis) and provided to designated unblinded recipients (i.e., pharmacist) at the clinical site.

Treatment Group	Drug
or oup	
A	Mepolizumab low (3 mg)
В	Mepolizumab low intermediate (6 mg)
С	Mepolizumab high intermediate (12 mg)
D	Mepolizumab high (24 mg)
Е	Reslizumab low (0.1 mg/kg)
F	Reslizumab low intermediate (0.2 mg/kg)
G	Reslizumab high intermediate (0.4 mg/kg)
Н	Reslizumab high (0.8 mg/kg)
I	Placebo

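### The AE tables should show placebo by route: one placebo column of 8 halves the expected rate of events that only one route of administration can cause

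*SAP*

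**What the plan says.** **AE summary.** SAP 7.7.1 organises TEAE incidence by system organ class and frequency, and states that it "will be summarized by seriousness, severity, relationship to treatment, and by treatment at onset of the TEAE". Protocol 5.9.8.1 has the same rule: "summarized by seriousness, severity, relationship to treatment, and by treatment at onset of the TEAE". Neither section mentions route of administration.

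**What counts as a treatment.** Protocol 5.8.1 introduces its list with "On Day 1, subjects will receive 1 of the following 9 treatments according to the randomization schedule", and placebo is one of the nine (Group I). The treatment tables in both documents show it as a single row of 8. SAP Section 5 analyses subjects by the dose and treatment they received and does not mention route.

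**Route.** SAP Attachment B states: "Mepolizumab will be administered subcutaneously and reslizumab will be administered intravenously". It adds that placebo is given by either route so as to match the active drug. Protocol 5.1.1 gives the split: "placebo will be administered either subcutaneously or intravenously (4 subjects each"). Protocol 5.8.1 repeats it: "Treatment Group I: Placebo, (4 subjects receive SC and 4 subjects receive IV").

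**Expected events.** For mepolizumab, Protocol 5.1.3 says: "The most common adverse reactions include headache, injection site reaction, back pain, and fatigue", at an incidence of at least 5%.

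**The concern.** The design includes a route-matched control: four placebo injections for the mepolizumab arms and four placebo infusions for the reslizumab arms. The AE plan makes no use of that matching. A programmer working from SAP 7.7.1 has nine treatment labels and would produce one placebo column with a denominator of 8.

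For most events this does no harm. For a reaction at the study-drug injection site it does, because the four subjects given an infusion have no such site. They add to the denominator but can never add to the numerator. The placebo rate is then too low for an event that the injection itself can cause and that the Protocol expects with mepolizumab. At stake is whether a reader of the safety tables attributes to the drug what belongs to the needle.

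**Working it through.** **Inputs from the documents**
- Placebo group size: "8 will be randomized to placebo" (Protocol 5.9.1).
- Split: 4 SC and 4 IV (Protocol 5.1.1 and 5.8.1).
- Active arms: 8 per dose (SAP 3.2), mepolizumab SC only and reslizumab IV only.

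**Reproducing the plan's figures.** 4 + 4 = 8, the stated placebo group. 9 × 8 = 72, the stated planned enrolment. Protocol 5.9.1 speaks of nine active arms plus 8 on placebo, which would give 9 × 8 + 8 = 80. SAP 3.2, with eight active arms plus placebo, agrees with 72. This slip does not affect the present point.

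**Assumption.** The documents give no placebo event rates. Let p be the true rate under the matched placebo route and q the rate under the other route. I use a range of p, and q = 0, p/2 or p.

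**Expected rate in a single placebo column**

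(4p + 4q) / 8 = (p + q) / 2

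Ratio to the matched rate = (1 + q/p) / 2:
- q = 0 (event impossible under the other route): 0.50
- q = p/2: 0.75
- q = p (equally likely under both routes): 1.00, no dilution

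**Size when q = 0.** If the drug's rate is d, the like-for-like difference is d − p and the displayed difference is d − p/2. The excess is overstated by p/2, whatever d is. The last column is (1 − p)⁴, the chance that none of the four matched subjects has the event.

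| Matched placebo rate p | Single-column rate p/2 | Overstatement | Chance of 0 events in 4 |
|---|---|---|---|
| 5% | 2.5% | 2.5 points | 81% |
| 10% | 5% | 5 points | 66% |
| 25% | 12.5% | 12.5 points | 32% |

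**As it would look in a table.** One event among the four matched subjects is 1/4 = 25%, shown as 1/8 = 12.5%. Two events are 2/4 = 50%, shown as 2/8 = 25%. With no events, both displays show 0%.

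**Precision of a same-route column** (exact 95% intervals): 0/4, 0 to 60%; 1/4, 0.6% to 81%; 2/4, 6.8% to 93%. The pooled 0/8 has an upper limit of 37%, but for a route-specific event part of that apparent precision comes from subjects who could not have had it.

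**Replacements.** Under Protocol 5.5.2 a replacement gets the treatment of the subject replaced, so the dosed split may not stay 4:4. With 5 SC and 4 IV the factors are 5/9 = 0.556 for SC-only events and 4/9 = 0.444 for IV-only events, instead of 0.50.

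**The case against.** **Pooling is not written.** Neither AE section says that SC and IV placebo are combined, and neither gives a denominator. This stands. Pooling follows from how treatment is defined, so the defect is that a needed display choice is left open and its default is the unhelpful one.

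**No AE comparison is planned.** Incidence is summarised descriptively, no endpoint in either document is a safety endpoint, and all data are listed (SAP Section 7), so a reader could rebuild the split. This stands too, and it confines the effect to the summary tables. Listings do not, however, correct a table that invites the wrong reading.

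**Four subjects tell us little.** True, as the intervals show. But a rate over 4 shows its weakness openly, while a rate over 8 hides it behind subjects not at risk.

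**Stronger readings that a reader might infer, and that the documents do not support**
- *All injection- or infusion-related placebo rates are halved.* Halving needs zero risk under the other route. Headache, fatigue and general hypersensitivity can occur under either. Any subject may have a catheter or venipuncture for blood sampling (Protocol 5.1.3 and 5.7.1.1), so sampling-site events can occur in every arm.
- *Infusion hypersensitivity is the main reslizumab risk, so the IV side matters as much.* Protocol 5.1.3 does not rank it so. It also lists malignancy, names oropharyngeal pain as the most common reaction, and reports anaphylaxis only after a second dose; this trial gives one dose. The SC injection site is the clear case.
- *The drug will look worse than placebo.* The overstatement is an expectation. At a 5% or 10% rate the likeliest placebo result is no event, and then both displays agree.

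**Conclusion.** The point holds as a minor one. If SAP 7.7.1 is followed as written, the single placebo column shows an expected rate of exactly half the at-risk rate for events that only one route of study-drug administration can cause. A descriptive reading then overstates the drug's excess by half the matched-placebo rate: 2.5 points at 5%, 5 points at 10%.

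This rests on three things: one placebo column, a 4:4 dosed split, and no risk of the event under the other route. The rates are assumed. Among the reactions the Protocol names, injection-site reaction with mepolizumab is the one clearly affected. No planned test, interval or endpoint depends on it.

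**What to change.** In SAP 7.7.1, add that TEAEs are shown for SC placebo, IV placebo and pooled placebo, each with the number actually dosed as denominator. State that study-drug administration-site events, and any others tied to one route, are read against same-route placebo, and that systemic events are read against the pooled column. Align Protocol 5.9.8.1 if it is amended.

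The cost is two extra columns and no new data. The display reveals nothing new about route, which Protocol 5.8.6 already leaves unblinded. The drawback is that same-route rates rest on about four subjects each; a table footnote should say so, so that 0/4 is not read as absence of risk.

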7.7.2 Clinical Laboratory Tests

Clinical laboratory results (hematology, serum chemistry, and urinalysis) will be summarized using descriptive statistics (number of subjects, mean, SD, minimum, median, and maximum). Clinical laboratory results will be classified as normal or abnormal, according to the reference ranges of the individual parameter. No statistical testing will be performed on clinical laboratory data.

7.7.3 Vital Sign Measurements

Vital sign measurements and changes from Baseline will be summarized using descriptive statistics (number of subjects, mean, SD, minimum, median, and maximum) by treatment and time point.

7.7.4 Safety 12-lead Electrocardiograms

The incidence of pathological ECG interpretive statements at Baseline and during treatment will be assessed among the treatments.

7.7.5 Physical Examinations

Physical examination findings will be presented in a data listing, and abnormal physical examination findings will be recorded as AEs.

7.7.6 Other Safety Data

All concomitant medication usage and medications that changed in daily dose, frequency, or both since the subject provided informed consent will be summarized for each subject.

8. Data Quality Assurance

Completed eCRFs are required for each subject randomly assigned to study drug. Electronic data entry will be accomplished through the ClinSpark® remote electronic data capture system, which allows for on-site data entry and data management. This system provides immediate, direct data transfer to the database, as well as immediate detection of discrepancies, enabling site coordinators to resolve and manage discrepancies in a timely manner. Each person involved with the study will have an individual identification code and password that allows for record traceability. Thus, the system, and subsequently any

investigative reviews, can identify coordinators, investigators, and individuals who have entered or modified records.

Furthermore, the investigator retains full responsibility for the accuracy and authenticity of all data entered into the electronic data capture system. The completed dataset and their associated files are the sole property of the sponsor and should not be made available in any form to third parties, except for appropriate governmental health or regulatory authorities, without written permission of the sponsor.

Attachment A. Pharmacokinetic, Pharmacodynamic, and Biomarker Sample Collection Schedule

Pharmacokinetic Sample Collection

Pharmacokinetic blood samples (5 mL) for determination of mepolizumab and reslizumab concentration will be collected and processed for serum at the following time points:

- Day 1: 0 (pre-dose), 1, 4, 12, and 24 h (0 h, Day 2)
- Day 3, 4, 5, 6, 7, 8, 9, 10, 11, 12, 13, 14, 21, 28, 35, 42, 49, 56, 63, 93, and 123

Blood samples will be collected by direct venipuncture or by inserting an IV catheter into the subject's forearm region. Each blood sample will be labeled with subject number, study number, study day, time point, event, and a barcode that matches that belonging to the subject.

Pharmacodynamic Sample Collection

Blood samples (5 mL) for primary pharmacodynamic biomarker (eosinophils) assessment will be collected at the following time points:

- Screening (Day -21 to -2)
- Day -1 (check-in)
- Day 1: 0 (Pre-dose), 24 h (0 h, Day 2)
- Day 3, 4, 5, 6, 7, 8, 9, 10, 11, 12, 13, 14, 21, 28, 35, 42, 49, 56, 63, 93, and 123

Blood samples will be collected by direct venipuncture or by inserting an IV catheter into the subject's forearm region. Each blood sample will be labeled with subject number, study number, study day, time point, event, and a barcode that matches that belonging to the subject.

Exploratory PD Biomarkers

Exploratory PD biomarkers will be evaluated using plasma proteomics and small RNA transcriptomics. Whole blood samples (5 mL) will be collected and processed for plasma at the following time points:

- Day -1 (check-in)
- Day 1: 0 (pre-dose), 0.5, 1, 2, 3, 4, 6, 9, 12, 18 and 24 h (0 h, Day 2)
- Day 3, 4, 5, 6, 7, 8, 9, 10, 11, 12, 13, 14, 21, 28, 35, 42, 49, 56, 63, 93, and 123

Blood samples will be collected by direct venipuncture or by inserting an IV catheter into the subject's forearm region. Each blood sample will be labeled with subject number, study number, study day, time point, event, and a barcode that matches that belonging to the subject. All blood samples will be processed for preparation of plasma.

Attachment B. Randomization Schedule

Subjects will enter the study clinic for check-in procedures the day before study drug administration of the first period (Day -1). Mepolizumab will be administered subcutaneously and reslizumab will be administered intravenously. Placebo will be administered subcutaneously or intravenously to match study drug. On Day 1, subjects will receive their assigned treatment according to the randomization schedule generated by the randomization biostatistician (unblinded and unaffiliated with study data analysis) and provided to designated unblinded recipients (i.e., pharmacist) at the clinical site.

Treatment Group	Drug
or oup	
A	Mepolizumab low (3 mg)
В	Mepolizumab low intermediate (6 mg)
С	Mepolizumab high intermediate (12 mg)
D	Mepolizumab high (24 mg)
Е	Reslizumab low (0.1 mg/kg)
F	Reslizumab low intermediate (0.2 mg/kg)
G	Reslizumab high intermediate (0.4 mg/kg)
Н	Reslizumab high (0.8 mg/kg)
I	Placebo
